**NOTE: all timed procedures are with respect to START of study drug infusion.**

AE= adverse event; BP = blood pressure; con med = concomitant medications; CRU = clinical research unit; ECG = electrocardiogram; FU = Follow-up; HIV = human immunodeficiency virus; Hep = Hepatitis; PR = pulse rate; PK = pharmacokinetics; RR = respiratory rate.

\*Day 3 is the completion visit. Assessments to be performed on Day 3 prior to discharge from the CRU or at early termination; physical exam, vital sign assessments, clinical laboratory tests and ECG.

A full physical exam will be conducted at screening and an abbreviated physical exam will be conducted on Day -1 and Day 3.

Pre-dose and 1.5 h post infusion start ECGs will be triplicate ECGs (Triplicate ECGs will be performed approximately 1 minute apart).

Clinical laboratory samples include: hematology, chemistry, coagulation parameters PT/INR/aPTT, and urinalysis.

For female subjects – Serum pregnancy test at screening and urine pregnancy test at admission, both must be negative to enroll in the study.

FSH and estradiol levels will be assessed in postmenopausal females to confirm status.

IV infusion will occur at approximately 8:00 am, following completion of a low-fat breakfast. Infusion will over an approximately 60 minute period. Infusion stop time will have a time window of  $\pm 5$  minutes.

Time windows: Vital signs and ECGs: Pre-dose: within 60 min prior dosing; post-dose to  $\leq 12$  h: ( $\pm 15$  min);  $\geq 24$  h: ( $\pm 30$  min).

PK sampling: pre-dose (-60 min),  $< 2$  h ( $\pm 5$  min), 2 to  $<24$  h ( $\pm 10$  min), 24, 36 and 48 h ( $\pm 15$  min).

Injection site assessments: pre-dose (-60 min),  $\leq 24$  h ( $\pm 30$  min).

## **Randomization**

Each subject who signs an informed consent form (ICF) upon Screening will be assigned a unique subject identification (ID) number. The subject ID which will remain unchanged throughout the study. In case of screening failure, the subject ID will not be reused. If eligible for entry into the study, each subject will be assigned a randomization number and receive the study treatment assigned to the corresponding randomization number. Randomization subject numbers are pre-assigned on Day 1 based on order of arrival at the clinic for admission to the study.

This is a double-blind study with regard to treatment (HF1K16 or placebo) at each dose level cohort. The following personnel will have access to the randomization scheme: unblinded statistician who provides the randomization scheme, pharmacy personnel preparing IP on site, and Bioanalytical personnel analyzing the PK samples (refer to the Section 7 regarding blinding of treatment by Bioanalytical team prior to sending for the PK parameters to be estimated). The Bioanalytical team will only provide drug-treated subject concentrations in a blinded fashion. The randomization scheme will be kept in a secure location until the end of the study.

For this study, subjects will be randomized with a 3:1 ratio for HF1K16 and placebo. The escalated doses will be defined according to the emerging safety and tolerability data (refer to the protocol for further information).

A four-digit randomization number will include the first digit for the cohort number and the last 3 digits for the subject number. If a subject becomes ineligible and needs to be replaced, the replacement subject will have the same treatment to maintain the 3:1 ratio of active to placebo for the cohort.

At the initiation of the study, the study site will be instructed on the method for breaking the blind. Blinding codes should be broken only in emergency situations for reasons of subject safety.

### **3.1 Sample size justification**

No formal sample size calculation has been performed. Sample sizes for this study are chosen based on feasibility of providing adequate information at each dose level.

### **3.2 Data handling**

#### **General:**

Summaries for continuous variables will include the descriptive statistics for number of subjects (n), mean (arithmetic and geometric), standard deviation (SD), minimum (min), median, and maximum (max), coefficient of variation (CV, arithmetic, and geometric). Summaries for categorical (discrete) variables will include the descriptive statistics frequency and percentage.

Conventions for presentation of numerical data:

Minimum and maximum values will be presented to the same number of decimal places as the electronic case report form (eCRF) data. Means and medians will be presented to one more

decimal place than the eCRF data. Standard deviations will be presented to two more decimal places than the eCRF data.

### **Baseline**

For comparison against baseline (e.g., for vital signs), baseline is considered as the last available assessment or value on or before the first treatment in the study.

### **Drug Concentrations and PK Parameter:**

Plasma concentration of tretinoin and 4-oxotretinoin, will be displayed in listings as received from the bioanalytical laboratory.

In general, individual concentrations and PK parameters and summary values will be displayed using 3 significant figures regardless of the decimal point position as follows:

- (1) Values  $\geq 0.0001$  and  $< 1$  will be reported to 4 decimal places (e.g., 0.0123).
- (2) Values  $\geq 1$  and  $< 10$  will be reported to 2 decimal places (e.g., 1.02).
- (3) Values  $\geq 10$  and  $< 100$  will be reported to 1 decimal places (e.g., 10.2).
- (4) Values  $\geq 100$  and  $< 1000$  will be reported to as a whole integer (e.g., 100).
- (5) Values  $\geq 1000$  or equal to 0 will be reported as a whole integer (e.g., 1000).

Values for  $T_{max}$  will be reported to 2 significant places.

### **3.3 Study Subjects**

#### **Subject disposition**

Eligibility Status for the study will be listed for all subjects enrolled in the study.

Subject disposition will be summarized using number and percent of subjects who complete the study. Subject disposition and completion status will be listed for all enrolled subjects.

#### **Protocol deviations**

Key protocol deviations will be listed by subject and treatment.

Protocol deviations will be identified prior to database lock and may include but are not limited to significant violations of inclusion/exclusion criteria, noncompliance of the trial treatment taken, use of prohibited medications and not following clinical trial protocol procedures that may affect evaluation of the PK statistical analysis. Further programmatic edit checks on the time points and allowed windows may be conducted depending on the data.

### **4 Statistical Analysis Populations**

#### **4.1 Randomized Population:**

All enrolled participants assigned a random number.

#### **4.2 Safety Population**

All randomized subjects who have received at least one dose of study drug.

#### **4.3 Pharmacokinetic (PK) Population:**

All subjects who receive active drug, have no major protocol violations, and have sufficient PK data to obtain reliable estimates of the key PK variables. Subjects in the PK population will be referred to as evaluable subjects.

#### **4.4 Subject Demographics/other Baseline Characteristics**

Demographic and baseline characteristics will be summarized for the Randomized Population. The demographic and baseline characteristics will consist of age, gender, race, ethnicity, height (cm), weight (kg), and BMI (kg/m^2). Demographic and baseline characteristics will be summarized by treatment. Demographic and baseline characteristics will be listed as well.

The age is a calculated parameter. Age at baseline of the entire study will be calculated using the subject's date of birth and the subject's informed consent date.

Continuous variables (e.g., age, height, weight, BMI) will be summarized by n, mean, standard deviation (SD), minimum, median, and maximum. Frequencies and percentages will be used to describe categorical (discrete) variables (e.g., gender, race, and ethnicity).

#### **4.5 General Medical History and Non-Drug Therapies**

The presence/absence of any current medical condition and/or other significant medical history will be coded using Medical Dictionary for Regulatory Activities (MedDRA) Version 24 or higher. Any non-drug therapies that are incurred during the course of the study will also be coded using MedDRA, as appropriate. Medical history will be listed by treatment and subject. Non-drug therapies will be listed by subject (unless these are not present in the database).

#### **4.6 Prior and Concomitant Medications**

All prescription medications taken in the 30 days prior to dosing or during the study period will be documented in the subject's eCRF.

Prior and concomitant medications will be coded using the current version of WHO Drug Enhanced Dictionary, version March 2021 or later, and listed by reported term and Anatomical Therapeutic Class classification. Medications will be listed by treatment and subject including the start and end dates and times, dose, dose unit, route, frequency, dose form, and indication.

### **5 Pharmacokinetic Analysis**

Plasma samples for the PK analysis of HF1K16 (free tretinoin and liposome encapsulated tretinoin) will be collected relative to Day 1 dosing.

Blood samples for plasma tretinoin and 4-oxotretinoin PK analysis will be collected within 60 minutes prior to start of infusion, and 0.5, 1, 1.5, 2, 4, 6, 9, 12, 24, 36, and 48 hours relative to start of infusion.

A deviation within allowable time windows will not be considered as a protocol deviation as long as the actual sampling time is recorded, refer to the following [Table 3](#) for allowed time window deviations.

**Table 3 Plasma Concentration Time Point Deviations**

Time Points	Deviation Window
Pre-dose, pre-infusion	Within 60 minutes prior to dosing
< 2h post-dose	± 5 minutes
2 hours to ≤ 24 hours	± 10 minutes
24, 36, and 48 hours	± 15 minutes

### 5.1 Plasma Concentrations

Plasma tretinoin and 4-oxotretinoin concentrations will be expressed in ng/mL, listed at each actual timepoint by subject and treatment, and summarized by treatment at each nominal timepoint using descriptive statistics (arithmetic mean, SD, coefficient of variation (CV%), geometric mean, median, min and max values and geometric CV%). All values below the quantification limit (BQL) will be labeled as such in the concentration listings and treated as zero for the concentration data summary statistics.

Linear and semi-log scale plots of mean concentration levels of plasma tretinoin and 4-oxotretinoin and individual subject concentrations versus time will be presented for the PK Population.

### 5.2 Pharmacokinetic Parameters

All PK calculations will be performed using Phoenix WinNonlin Version 8.1 (Certara USA, Inc., Princeton, USA). Plasma PK parameters for tretinoin and 4-oxotretinoin will be calculated with the IV infusion model non-compartmental analysis (NCA) with actual times of blood sample collection.

For PK parameter calculations, concentrations below BQL will be set to zero if they occur prior to the first or after the last quantifiable concentration and will be set to missing for data points in between.

Pharmacokinetic (PK) parameters  $AUC_{last}$ ,  $AUC_{inf}$ ,  $C_{max}$ ,  $T_{max}$ , MRT,  $K_{el}$ ,  $t_{1/2}$ ,  $CL/F$ , and  $V_zF$  for tretinoin and 4-oxotretinoin will be listed by treatment, subject and summarized by treatment with descriptive statistics as listed above for concentration data for the PK Population.

$AUC_{last}$  will be estimated using the linear trapezoidal method from time 0 hour to time  $t$ .  $AUC_{inf}$  will be calculated as the sum of  $AUC_{last}$  and  $AUC_{t-inf}$ , where  $t$  is the time corresponding to the last measurable serum concentration.  $AUC_{t-inf}$  will be calculated as  $C_t / \lambda_z$ , where  $C_t$  is the last measurable serum concentration and  $\lambda_z$  is the terminal phase rate constant. The value of  $\lambda_z$  will

be estimated by least-squares regression of the terminal log-linear serum concentration-time profile.

No value of  $K_{el}$ ,  $AUC_{inf}$ ,  $t_{1/2}$ ,  $V_zF$ , or  $CL/F$  will be reported for cases that do not exhibit a terminal log-linear phase in the concentration versus time profile with at least three timepoints. If the adjusted R-squared value (Rsq\_adjusted) is < 0.80, the PK analyst may evaluate if other time points are more appropriate for the calculation of  $\lambda_z$ , otherwise no value of  $K_{el}$ ,  $AUC_{inf}$ ,  $t_{1/2}$ ,  $V_zF$  and  $CL/F$  will be reported.

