### **5.3 Dose Proportionality**

For the dose cohorts Up to 3 mg/m^2, 6 mg/m^2, 10 mg/m^2, and 13 mg/m^2, a dose proportionality regression assessment for log-transformed  $C_{max}$ ,  $AUC_{0-last}$ , and  $AUC_{0-inf}$  and log-transformed dose will be analyzed using a power model:  $\ln(\text{PK parameter}) = \mu + \beta \times \ln(\text{dose})$  will be conducted for the free tretinoin and liposome encapsulated tretinoin. The 90% confidence intervals (CI) around the slopes ( $\beta$ ) from each of these regression analyses will be obtained from the model and presented. Plots of the log-PK parameter by log-dose ( $AUC_{last}$ ,  $AUC_{inf}$ , and  $C_{max}$ ) will be produced for the dose cohorts for the PK Population.

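### The SAP's PK sections name tretinoin and 4-oxotretinoin, but the protocol and the SAP's own dose-proportionality model name free and liposome encapsulated tretinoin

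*SAP*

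**What the plan says.** Six SAP statements name tretinoin and 4-oxotretinoin:

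- SAP 3.2, on drug concentrations: "Plasma concentration of tretinoin and 4-oxotretinoin, will be displayed in listings as received from the bioanalytical laboratory".
- SAP 5, second paragraph: "Blood samples for plasma tretinoin and 4-oxotretinoin PK analysis will be collected within 60 minutes prior to start of infusion".
- SAP 5.1, listings and summaries: "Plasma tretinoin and 4-oxotretinoin concentrations will be expressed in ng/mL, listed at each actual timepoint by subject and treatment".
- SAP 5.1, plots: "Linear and semi-log scale plots of mean concentration levels of plasma tretinoin and 4-oxotretinoin and individual subject concentrations versus time".
- SAP 5.2, calculation of parameters: "Plasma PK parameters for tretinoin and 4-oxotretinoin will be calculated with the IV infusion model non-compartmental analysis (NCA".
- SAP 5.2 again, where nine parameters are to be listed and summarised for the same pair.

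Two SAP statements name the two forms of the drug:

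- SAP 5, opening sentence: "Plasma samples for the PK analysis of HF1K16 (free tretinoin and liposome encapsulated tretinoin) will be collected relative to Day 1 dosing".
- SAP 5.3, on the power model: "will be conducted for the free tretinoin and liposome encapsulated tretinoin".

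The protocol names free and liposome encapsulated tretinoin wherever it specifies PK work: in the synopsis, 12.1 (blood collection), 12.4 (assay), 12.5 (non-compartmental analysis) and 14.3 (summaries, plots, power model). Protocol 14 says the SAP will present any changes to the analyses the protocol specifies. SAP 9 states that there are none.

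**The concern.** The SAP gives two different analyte lists for one chain of analysis. Concentrations are listed, summarised, plotted and put through non-compartmental analysis under one list. The resulting parameters are then modelled under the other.

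Two consequences follow from the text alone. First, the encapsulated form has no named concentration summary, plot or parameter output in SAP 5.1 and 5.2, although SAP 5.3 needs its Cmax and AUC values. For a liposomal product, whose stated rationale in protocol 5.1 is slower clearance through encapsulation, the split between free and encapsulated drug is central to describing the PK. Second, 4-oxotretinoin enters the analysis with no protocol assay behind it and no declaration that it has been added.

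Timing matters too. SAP 1 says the output shells are followed once the SAP is signed, with only minor changes after it is final. A wrong analyte list is easy to correct before unblinding. Corrected later, it becomes a post hoc change to what is analysed.

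**Working it through.** The plan gives no figure to reproduce, so the check sets the passages side by side.

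| Step | SAP | Protocol |
|---|---|---|
| Sampling | 5, opening: free and encapsulated; 5, second paragraph: tretinoin and 4-oxotretinoin | 12.1: free and encapsulated |
| Assay | no analyte stated | 12.4: free and encapsulated |
| Concentration listings | 3.2, 5.1: tretinoin and 4-oxotretinoin | synopsis, 14.3: free and encapsulated |
| Concentration summaries | 5.1: tretinoin and 4-oxotretinoin | synopsis, 14.3: free and encapsulated |
| Plots | 5.1: tretinoin and 4-oxotretinoin | synopsis, 14.3: free and encapsulated |
| Non-compartmental analysis | 5.2: tretinoin and 4-oxotretinoin | synopsis, 12.5: free and encapsulated |
| Parameter listings and summaries | 5.2: tretinoin and 4-oxotretinoin | synopsis, 14.3: free and encapsulated |
| Power model | 5.3: free and encapsulated | synopsis, 14.3: free or encapsulated |

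**Count of SAP statements.** Tretinoin and 4-oxotretinoin: 1 (3.2) + 1 (5) + 2 (5.1) + 2 (5.2) = 6. Free and encapsulated: 1 (5, opening) + 1 (5.3) = 2. Total: 6 + 2 = 8.

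**Does other SAP text settle the matter?** It does not.

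- The glossary has no entry for tretinoin.
- SAP 2.4 lists the secondary PK endpoints without naming an analyte, so SAP 5.2 alone decides what they are computed for.
- SAP 9 declares no change.

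**What holds whatever tretinoin means.** 4-oxotretinoin is absent from the available protocol text and is not an input to the SAP 5.3 model. Yet SAP 5.2 asks for all nine parameters for it, including clearance and volume. Those two need a dose of the analyte, and the protocol gives doses of HF1K16 only, with tretinoin as the active substance.

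**What depends on what tretinoin means.** Whether SAP 5.2 actually yields the two sets of parameters that SAP 5.3 uses. The SAP text leaves this open.

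**Separate minor point.** The synopsis asks for concentrations and parameters of baseline-subtracted free tretinoin and of the encapsulated form. The matching sentence in protocol 14.3 omits the subtraction, and the SAP does not mention it. No size is attached here: the documents give no human free-tretinoin AUC for this product and no assay quantification limit.

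**The case against.** The strongest defence is that tretinoin in SAP 5.1 and 5.2 is shorthand for both forms reported separately. The opening sentence of SAP 5 supports this, as do SAP 5.3 and protocol 12.4 and 12.5. That is a reasonable guess at the intent. It is not a definition, and it does not explain 4-oxotretinoin, which stays in six statements with no protocol source.

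The defence is right about scope. PK is the secondary objective, no primary safety analysis uses these sections, and dose proportionality is reported as a slope with a 90% confidence interval and no acceptance criterion. The output shells were not available, and they may already name the right analytes.

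A reader might infer three stronger things, none of which the documents support:

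- **That half or all of the dose-proportionality fits have no input.** There are 3 parameters x 2 forms = 6 fits. The number lacking an input from SAP 5.2 is 0 if tretinoin means both forms, 3 if it means one, and 6 if it means a single total. The SAP does not choose between these readings, no total-drug assay is described, and the surrounding text leans towards the first. The count therefore measures the ambiguity and not a known loss.
- **That the encapsulated form will not be measured or analysed.** Protocol 12.1, 12.4 and 12.5 say that it will.
- **That unsubtracted baseline will bias the slopes materially, or that the SAP already prescribes a subtraction.** The size would rest on assumed baseline fractions. The SAP's baseline wording ("baseline is considered as the last available assessment or value on or before the first treatment in the study") is a general rule for change from baseline, with vital signs as its example, and not a PK correction.

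**Conclusion.** The contradiction is real, and the SAP is wrong as written. It names an analyte that the protocol does not assay, and in SAP 5.1 and 5.2 it does not name the encapsulated form that its own model uses. It also says that nothing has changed.

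The extent is six of eight analyte statements in the SAP, covering all listings, summaries, plots and parameter estimation for the secondary objective. The primary safety objective is untouched. Protocol 12.5 specifies the analysis of both forms, so the error is confined to the SAP.

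This rests on the documents alone. It assumes that the removed or redacted protocol text does not introduce 4-oxotretinoin. Whether any wrong table would be produced cannot be judged without the shells. The baseline-subtraction mismatch is a minor drafting inconsistency, with no magnitude claimed.

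**What to change.** 1. Ask the bioanalytical laboratory which analytes are assayed.
2. If they are those in protocol 12.4, replace tretinoin and 4-oxotretinoin with *free tretinoin and liposome encapsulated tretinoin* at six places: SAP 3.2 (drug concentrations), SAP 5 (second paragraph), SAP 5.1 (twice) and SAP 5.2 (twice). SAP 5.2 then supplies the inputs to SAP 5.3.
3. If 4-oxotretinoin is also measured, keep it only as an additional analyte, declared in the protocol and in SAP 9.
4. Check the output shells for the same wording and correct them if needed.
5. Reconcile the protocol synopsis with protocol 14.3 on baseline subtraction. If subtraction is kept, state the method in the SAP.

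The cost is one query and some wording changes before unblinding. No new samples are needed if the assays run as protocol 12.4 states. If they do not, the cost depends on the laboratory's answer.

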12. Taken any prescription or non-prescription drugs and herbal medication known to be CYP450 inducers, inhibitors, and substrates within 14 days prior to screening (See [Appendix B](#));
13. Taken daily Vitamin A supplement within 3 months prior to screening;
14. Major surgery or hospitalization within 6 months prior to screening that in the Investigators opinion would put the subject or study conduct at risk;
15. A history of prescription drug abuse, or illicit drug use within 9 months prior to screening;
16. A history of alcohol abuse according to medical history (≥ 2 drinks per day for male and ≥ 1 drink per day for female) within 9 months prior to screening;
17. A positive screen for alcohol, drugs of abuse at screening or admission;
18. An unwillingness or inability to comply with food and beverage restrictions during study participation;
19. Use of over-the-counter (OTC) medication within 7 days, and/or herbal medications (including herbal teas, garlic extracts) within 7 days prior to first dose of study drug;
20. Have a history of allergic reactions (either spontaneous or following drug administration) to ATRA or to any of the excipients or related compounds, including vitamin A;
21. Any condition or finding that in the Investigators opinion would put the subject or study conduct at risk if the subject were to participate in the study.

Investigational product, dosage, and mode of administration:

HF1K16 is a pegylated liposome formulation of tretinoin [All-Trans Retinoic Acid (ATRA)] supplied as 2 mg/mL, 10 mL/vial. Each subject will be administered a single IV infusion of HF1K16 over a period of approximately 60 minutes.

Duration of Study:

The total duration of participation in the study for each subject is up to 38 days, including a screening period of up to 28 day.

Reference therapy:

Placebo will be sterile saline (0.9% sodium chloride) for IV infusion.

Criteria for evaluation:

Safety:

Safety assessments will include monitoring of AEs, vital signs (blood pressure, pulse rate, respiration rate, oral temperature), clinical laboratory findings (chemistry, including LDL-C, HDL-C, triglycerides, total cholesterol, AST and ALT; coagulation parameters PT/INR and aPTT; hematology and urinalysis), resting 12-lead ECGs, physical examination findings (including evaluation of skin) and injection site assessment.

Pharmacokinetics:

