4 LIST OF ABBREVIATIONS

The following abbreviations and specialist terms are used in this study protocol.

Abbreviation or special term	Explanation
AE	Adverse Event
ALT	Alanine Transaminase
APL	Acute Promyelocytic Leukemia
AST	Aspartate Transaminase
ATRA	All-Trans Retinoic Acid
aPTT	Activated Partial Thromboplastin Time
AUC	Area Under the Curve
AUC _{last}	AUC up to the last measurable concentration
AUC _{inf}	AUC from time 0 to infinity
BMI	Body Mass Index
CI	Confidence Interval
CL/F	Total systemic clearance after oral administration
C _{max}	Maximum Plasma Concentration
CRO	Clinical Research Organization
CRU	Clinical Research Unit
CTCAE	Common Terminology Criteria for Adverse Events
DC	Dendritic Cell
DMP	Data Management Plan
ECG	Electrocardiogram
eCRF	Electronic Case Report Form
FDA	Food and Drug Administration
FSH	Follicle-Stimulating Hormone
GCP	Good Clinical Practice
GLP	Good Laboratory Practice
HCV	Hepatitis C Virus
HDL-C	High Density Lipoprotein - Cholesterol
HED	Human Equivalent Dose
HIV	Human Immunodeficiency Virus
IB	Investigator's Brochure
ICF	Informed Consent Form
INR	International Ratio
IRB	Institutional Review Board
IV	Intravenous
K _{el}	Apparent terminal elimination rate-constant
LC-MS/MS	Liquid Chromatography-Tandem Mass Spectrometry
LDL-C	Low Density Lipoprotein - Cholesterol
MedDRA	Medical Dictionary for Regulatory Activities
MDSC	Myeloid Derived Suppressor Cell
MRT	Mean Residence Time
NASH	Non-Alcoholic Steatohepatitis

Abbreviation or special term	Explanation
NOAEL	No Observed Adverse Effect Level
OTC	Over the Counter
PE	Physical Examination
PHI	Patient Health Information
PK	Pharmacokinetic(s)
PT	Prothrombin Time
PT	Preferred Term
RA	Retinoic Acid
RAS	Retinoic Acid Syndrome
RBC	Red Blood Cell
SAD	Single Ascending Dose
SAE	Serious Adverse Event
SAP	Statistical Analysis Plan
SDV	Source Data Verification
SMC	Safety Monitoring Committee
SOC	System Organ Class
SOP	Standard Operating Procedure
TB	Total Bilirubin
T _{max}	Time to maximum plasma concentration
T _{1/2}	Terminal Half-Life
ULN	Upper Limit of Normal
WHO	World Health Organization

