12.5 Pharmacokinetic Parameters

The plasma concentration time data for free tretinoin and liposome encapsulated tretinoin will be analyzed using non-compartmental methods. Actual dosing and sampling times will be used for PK analyses. The primary PK parameters of interest are: C_{max} , T_{max} , $t_{1/2}$, AUC_{last} . Additional PK parameters include AUC_{inf} , MRT, CL/F, V_zF and K_{el} .

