## Glossary and Abbreviations

Abbreviation	Term
AE	Adverse Event
ALP	Alkaline Phosphatase
ALT	Alanine Aminotransferase
AST	Aspartate Aminotransferase
AUC last	AUC from Time Zero to Time of Last Measurable Concentration
AUC inf	Area Under the Concentration-Time Curve from Zero Up to Infinity with Extrapolation of the Terminal Phase
BMI	Body Mass Index
BP	Blood Pressure
BQL	Below Quantitation Limit
CI	Confidence interval
C max	Observed Maximum Serum Concentration
CL/F	Apparent Total Plasma Clearance of Drug
CRU	Clinical research unit
CTCAE	National Cancer Institute Common Terminology Criteria for Adverse Events
CV	Coefficient of Variation
D	Day
DLT	Dose limiting toxicity
eCRF	Electronic Case Report Form
ECG	Electrocardiogram
FCS	Frontage Clinical Services
FSH	Follicle Stimulating Hormone
λ z	Terminal elimination rate constant
h or hr	Hour (s)
ICF	Informed consent form
ID	Identification
K el	Terminal elimination rate constant
LLOQ	Lower limit of quantification
Max	Maximum
MedDRA	Medical Dictionary for Regulatory Activities
Min	Minimum
mg	Milligram(s)
mL	Milliliter(s)

Abbreviation	Term
MRT	Mean residence time
N	Sample size
NCA	Non-compartmental analysis
ng	Nanogram(s)
PK	Pharmacokinetic(s)
PP	Pharmacokinetic parameter
PR	Pulse rate
RR	Respiratory rate
SAD	Single Ascending Dose
SAE	Serious Adverse Event
SAP	Statistical Analysis Plan
SD	Standard deviation
SE	Standard error of the mean
SMC	Safety Monitoring Committee
T max	Time to reach maximum concentration
t 1/2	Terminal half-life of elimination
TEAE	Treatment Emergent Adverse Event
TLF	Tables, Listings, Figures
V zF	Volume of distribution during terminal phase
WHO	World Health Organization

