#### 2.4 Secondary endpoints

- Pharmacokinetics (PK) in treated subjects, including:
  - Peak concentration ( $C_{max}$ )
  - Time to peak ( $T_{max}$ )
  - Area under the concentration-time curve ( $AUC_{inf}$ ,  $AUC_{last}$ )
  - Terminal elimination rate constant ( $K_{el}$ )
  - Elimination half-life ( $t^{1/2}$ )
  - Apparent Clearance (CL/F)
  - Volume of distribution (VzF)
  - Mean Residence Time (MRT)

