### **9 Changes from pre-specified analyses**

There are no changes from the planned analyses for this study.

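### SAP 5.2 reports CL/F and VzF for 4-oxotretinoin, which is not infused; both values carry an unmeasured conversion fraction and should be dropped for that analyte.

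*SAP*

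**What the plan says.** SAP 5.2 applies one infusion-model non-compartmental analysis to tretinoin and 4-oxotretinoin alike. It names AUClast, AUCinf, Cmax, Tmax, MRT, Kel, t1/2, CL/F and VzF, and says that these "for tretinoin and 4-oxotretinoin will be listed by treatment, subject and summarized by treatment with descriptive statistics". It makes no exception by analyte. SAP 2.4 lists CL/F and VzF among the secondary endpoints.

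The infused product is described in the protocol Synopsis: "HF1K16 is a pegylated liposome formulation of tretinoin". Protocol 12.5 plans the parameters for other analytes: "The plasma concentration time data for free tretinoin and liposome encapsulated tretinoin will be analyzed using non-compartmental methods". 4-oxotretinoin does not appear in the protocol.

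CL/F is defined twice. The SAP glossary has "Apparent Total Plasma Clearance of Drug". The protocol's abbreviation list has "Total systemic clearance after oral administration".

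Protocol 14 says the SAP will present any changes to the analyses proposed there. SAP 9 states: "There are no changes from the planned analyses for this study".

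**The concern.** CL/F and VzF are each a dose divided by an exposure term. They describe an analyte's own disposition only if the dose in the numerator is a dose of that analyte, or a known fraction of another dose that becomes it. No 4-oxotretinoin is given, and no assessment measures how much is formed. The analyst has only the tretinoin dose to enter.

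The resulting table would be headed as clearance and volume for 4-oxotretinoin, under named secondary endpoints, but its values would mix elimination of 4-oxotretinoin with the extent of conversion from tretinoin. If conversion differs between subjects or dose groups, the table would show differences in clearance that did not occur. Neither definition of CL/F tells the reader that a conversion fraction is included.

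**Working it through.** The plan states no figure on this point, so there is none to reproduce. The check is an identity, illustrated with assumed values of f.

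**Inputs**
- Substance infused: tretinoin (protocol Synopsis). Its formula, from the chemical name given there, is C20H28O2, molar mass 300.44.
- 4-oxotretinoin: C20H26O3, molar mass 314.43. This is taken from its structure; the documents do not state it.
- Molar mass ratio: 314.43 / 300.44 = 1.047 (1.0465 before rounding).
- f, the fraction of the tretinoin dose that becomes circulating 4-oxotretinoin: not in the documents. Assumed range 10% to 50%.
- CL_m and V_m: the true clearance and volume of 4-oxotretinoin. Linear kinetics are assumed.

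**CL/F**

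The mass of 4-oxotretinoin formed is f × 1.047 × Dose, so AUC_m = f × 1.047 × Dose / CL_m.

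The reported value is Dose / AUC_m = CL_m / (f × 1.047), and its ratio to the truth is 1 / (f × 1.047).

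| f (assumed) | Reported / true CL | Reported CL/F if true CL_m = 20 L/h |
|---|---|---|
| 10% | 9.6 | 191.1 L/h |
| 20% | 4.8 | 95.6 L/h |
| 30% | 3.2 | 63.7 L/h |
| 40% | 2.4 | 47.8 L/h |
| 50% | 1.9 | 38.2 L/h |

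The last column comes from a numerical check with a 60-minute infusion and one compartment each for tretinoin and 4-oxotretinoin. It agrees with the formula. Two subjects with the same 4-oxotretinoin clearance but f of 20% and 40% would be reported with CL/F values differing by 4.78 / 2.39 = 2.0-fold.

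**VzF**

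Reported VzF = Dose / (λz × AUC_m) = CL_m / (f × 1.047 × λz). The true volume is CL_m / k_m, where k_m is the analyte's own elimination rate. The ratio is therefore [1 / (f × 1.047)] × (k_m / λz).

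If the terminal slope is the analyte's own elimination, k_m / λz = 1 and the factor is the same as for CL/F. If formation or release from the liposome is slower, λz is smaller than k_m and the error grows. Protocol 6.1.2 reports slow clearance of encapsulated drug and sustained concentrations in animals, so this case is plausible.

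An assumed example, leaving out the 1.047: CL_m = 10 L/h and V_m = 15 L give k_m = 10 / 15 = 0.667 /h. With a formation-limited slope of 0.25 /h:
- f = 10%: (10 / 0.1) / 0.25 = 400 L against a true 15 L
- f = 50%: (10 / 0.5) / 0.25 = 80 L, or 5.3 times the truth
- f = 100%: 10 / 0.25 = 40 L, still 2.7 times the truth

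**Extent**

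SAP 5.2 implies 9 parameters × 2 analytes × 4 dose groups = 72 summaries. CL/F and VzF for 4-oxotretinoin account for 2 × 4 = 8 of them.

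**The case against.** The best defence is that the SAP calls the parameter apparent, both in the glossary and in 2.4, and that the F already signals an unknown fraction. Dose divided by AUC for a formed product is a quantity of the same kind, and the SAP nowhere claims to estimate an absolute clearance of 4-oxotretinoin. On that view a footnote would do. Part of this stands: the value is a well-defined hybrid and it can be labelled. But the glossary ties it to clearance of the drug and the protocol to oral dosing, and neither brings in conversion from another substance. A table by analyte invites the wrong reading, and a footnote cannot supply f.

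It is also fair to say that the SAP is unsettled on its analytes. Section 5 names both pairs, 5.1 and 5.2 use tretinoin and 4-oxotretinoin, and 5.3 uses free and encapsulated tretinoin. If the sponsor resolves this by dropping 4-oxotretinoin, the point disappears. As written, 5.2 orders the calculation.

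The documents never call 4-oxotretinoin a product of tretinoin, so that relation is assumed. The point needs only that it is not the substance infused, which they support.

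A reader might infer that intravenous dosing justifies removing the F throughout. That does not hold for free tretinoin. The product is encapsulated drug, so the AUC of free tretinoin also depends on release from the liposome.

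**Conclusion.** The point holds for two parameters of one analyte. CL/F for 4-oxotretinoin would be 9.6 to 1.9 times its true clearance for f between 10% and 50%, and VzF would be off by at least that factor. These sizes rest on the assumed f, linear kinetics, and molar masses taken from structure. The direction and the confounding with f do not depend on the particular value of f chosen within that range.

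The consequence is limited to descriptive secondary tables. A reader might infer that dose escalation or dose proportionality is compromised, but the documents do not support that. The cap in Protocol 10.6 is on AUC, and the power model in SAP 5.3 uses Cmax and AUC for free and encapsulated tretinoin. Safety conclusions do not use these parameters.

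A reader might also infer that clearance of tretinoin itself will be wrong, because SAP 5.2 does not name the dose amount or unit. That is missing detail, not evidence of error. Protocol 11.3 keeps dose calculations in the pharmacy log, and Protocol 10.3 records infusion start, stop and interruption times. An infusion that stops at the early edge of its window may simply have emptied the bag. The exposure summary promised in Protocol 14.5 but absent from SAP 6.1 is likewise a clarification only.

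**What to change.** In SAP 5.2, report CL/F and VzF for tretinoin only. For 4-oxotretinoin keep AUClast, AUCinf, Cmax, Tmax, MRT, Kel and t1/2. If a measure of conversion is wanted, add the molar AUC ratio of 4-oxotretinoin to tretinoin. Keep the apparent labels, CL/F and VzF, for free tretinoin. In SAP 9, record 4-oxotretinoin as an analyte added since the protocol.

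While these sections are open, it would help to state the dose amount and unit used for tretinoin in 5.2, and to add the per-dose exposure summary to 6.1.

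The cost is a few SAP sentences. Eight summaries are removed, and no data, procedure, visit or sample size changes.
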